Assignment to condition. Upon completion of the baseline survey, participants will be individually randomized to receive either a brief Safety Planning Intervention (n=30), or the 3-session telehealth intervention (n=30). Participants will be randomized at a 1:1 ratio using a block randomization method (4 per block) to ensure equal sample sizes in each condition and to manage the flow of participants to the intervention condition. The allocation sequences will be prepared ahead of time using an online randomization program.

Intervention and control procedures. After randomization, participants will be guided to a private space and assisted to connect by video call to the nurse-counselor (based at KCMC). Upon connecting, control participants will receive the brief (20 minute) Safety Planning Intervention and intervention participants will complete the first of 3 telehealth-delivered counseling sessions. For intervention participants, the remaining sessions will be scheduled at two-week intervals. Patients unable to come to the clinic for followup sessions will be given the option to connect via video call or telephone call from the location of their choice. For participants in both conditions, prior to ending the call, the counselor will re-administer the C-SSRS and those at risk of suicide will be directly referred for psychiatric assessment and treatment to ensure their safety. Participants in both conditions will receive text message check ins from the counselors to inquire about their well-being and connect them to additional support as needed. Participants in both conditions will also have the opportunity to contact the telehealth counselors at any time during normal business hours for additional support throughout their participation in the study. These 'booster sessions' will be focused on assessing suicide risk, safety planning, and reinforcing prior session content.

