• If subjects who do not have the capacity to give legally effective consent are included, describe how diminished capacity will be assessed. Will a periodic reassessment occur? If so, when? Will the subject be consented if the decisional capacity improves?

Clinic nurses will assess the participant's capacity to provide consent prior to referring them to the study. Patients who lack the intellectual capacity to give legally effective consent, who are medically unstable, or who are in acute psychiatric distress, will not be enrolled and will instead be referred for appropriate care within the clinics. These participants will be screened for capacity again at their next HIV appointment, and will have the opportunity to enroll at that time if their decisional capacity has improved.

Study Interventions

• If not already presented in #4 above, describe study-related treatment or use of an investigational drug or biologic (with dosages), or device, or use of another form of intervention (i.e., either physical procedures or manipulation of the subject or the subject's environment) for research purposes.

Risk/Benefit Assessment

Include a thorough description of how risks and discomforts will be minimized (per 45 CFR 46.111(a) (1 and 2)). Consider physical, psychological, legal, economic and social risks as applicable. If vulnerable populations are to be included (such as children, pregnant individuals, imprisoned persons or cognitively impaired adults), what special precautions will be used to minimize risks to these subjects? Also identify what available alternatives the person has if he/she chooses not to participate in the study. Describe the possible benefits to the subject. What is the importance of the knowledge expected to result from the research?

Ethical considerations for the study will be grounded in recent NIMH guidance on Conducting Research with Participants at Elevated Risk for Suicide. All participants will provide written informed consent prior to participation and a decision not to participate will in no way influence the patient's eligibility for standard care at the clinic. We will continually monitor safety indicators, including suicide attempts and suicide deaths. In the unlikely event of (a) increases in suicidal behavior or (b) greater suicidality in the intervention condition as compared to control, the trial will be discontinued.

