Given this close monitoring of safety, we anticipate the risk to participants to be minimal. Potential risks to participants in this study include: 1) negative consequences if confidentiality of information obtained in the study are compromised (including subject identity as a research participant, information collected during assessments, or abstracted information from the medical record review); 2) unintended consequences (e. g., stigma and inadvertent HIV disclosure) resulting from participation in the telehealth intervention; and 3) distress or emotional reactions related to the study assessments or intervention sessions.

Confidentiality is of critical importance, and we will take many precautions to protect against the possibility of a breach of confidentiality. Our research team is very aware of the importance of maintaining strict confidentiality and has extensive experience dealing with sensitive information. All study staff will be well trained and will receive ongoing supervision in confidentiality and data security procedures, specifically in ethical conduct, confidentiality protection, review of medical records, mandated reporting, and other topics of human participant protection. Steps to protect against risks will be implemented as follows:

Prior to any data collection, all study staff will be trained in the protection of human subjects. As this study is specifically enrolling patients who are experiencing suicidal ideation, additional protections will be implemented to minimize risk of suicide. At the conclusion of all Aim 1 interviews and Aim 3 counseling sessions in both conditions (intervention or enhanced standard of care), the nurse-counselor will re-administer the C-SSRS measure of suicide risk. At the first study visit, we will provide all participants with a list of local resources for additional mental health support, including contact information for the health system's inpatient and outpatient psychiatry services.

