Feasibility and acceptability of the intervention will be described by retention patterns, participant satisfaction, fidelity, and implementation cost. *Participant satisfaction* will be measured using the Client Satisfaction Questionnaire⁹³ at the 3-month survey and defined as a mean score \geq 3 on a 1-4 scale. *Fidelit y* to the manual will be measured by TQS and deemed acceptable if mean scores are \geq 3 on a 0-4 scale. *Co st* of the intervention will be tracked, including the time for training, supervision, and actual costs incurred.

Potential efficacy will be assessed by analyzing differences by condition in primary outcomes (suicidality, HIV care engagement, viral load) and secondary outcomes (depression, social support, quality of life). The trial will not be powered to detect significant intervention effects or stable effect sizes; however, we will conduct these analyses to examine the potential for effects in a larger trial. Mixed-effects regression will be used to model pre-post differences within and between arms using a time by condition model specification (time, condition, and time*condition). Individual-level random intercepts will be used to account for correlation due to repeated measurement. This mixed-effects regression approach allows us to control for baseline outcome values that may not be balanced between groups due to small sample size, and may improve precision of treatment effect estimates. We will also generate parameter estimates and ranges of values to estimate power for a future larger clinical trial study.

Data & Safety Monitoring

• Summarize safety concerns, and describe the methods to monitor research subjects and their data to ensure their safety, including who will monitor the data, and the frequency of such monitoring. If a data monitoring committee will be used, describe its operation, including stopping rules and frequency of review, and if it is independent of the sponsor (per 45 CFR 46.111(a) (6)).

The Duke PI [name] will receive guidance on research with patients at-risk of suicide in monthly mentoring meetings with [name], a recognized expert in the field of suicide prevention research. During these meetings, Drs. [name] and [name] will review safety data from the study, including trends in suicidal ideation and any reported instances of suicidal behavior or death by suicide

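### Do the extra C-SSRS readings in the intervention arm bias the between-arm safety comparison or the discontinuation rule?

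*Combined protocol and SAP*

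**What the plan says.** In Design & Procedures, Aim 3, both arms start with a video call to the nurse-counselor. For control (n=30) this is a single 20-minute Safety Planning Intervention; for the intervention arm (n=30) it is the first of three sessions. On that call, "For participants in both conditions, prior to ending the call, the counselor will re-administer the C-SSRS". Anyone whom this reading shows to be in danger is sent on for psychiatric care. After the call, "For intervention participants, the remaining sessions will be scheduled at two-week intervals". The Risk/Benefit Assessment carries the same instruction, at the end of "Aim 3 counseling sessions in both conditions (intervention or enhanced standard of care), the nurse-counselor will re-administer the C-SSRS measure of suicide risk". The Preliminary Telehealth Model also puts a reading at the end of every session.

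Outside scheduled sessions the arms are treated alike. Both receive text check-ins and may request booster sessions that assess suicide risk. Data & Safety Monitoring adds a risk assessment whenever distress is reported between sessions.

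The discontinuation rule appears twice. The Risk/Benefit Assessment says "We will continually monitor safety indicators, including suicide attempts and suicide deaths" and then gives two triggers: (a) a rise in suicidal behaviour, and (b) "greater suicidality in the intervention condition as compared to control, the trial will be discontinued". Data & Safety Monitoring gives the same two triggers and adds a source to each: (a) is judged between baseline and the follow-up survey, and (b) on suicidality as that survey measures it. The same section has monthly meetings that review safety data, "including trends in suicidal ideation and any reported instances of suicidal behavior or death by suicide".

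The only time named for a follow-up survey is in Data Analysis & Statistical Considerations, for the satisfaction questionnaire: "at the 3-month survey and defined as a mean score".

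**The concern.** Surveillance is unequal by design. Between the first call and the survey, a trained counselor asks intervention participants about suicidality twice on a fixed schedule. Control participants have no scheduled C-SSRS in that period. An arm that is asked more often will report more, even at equal true risk.

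This touches the central safety claim, which is that participants will not be at increased risk of suicidal behaviour. It could also touch the rule that ends the trial. Read alone, the Risk/Benefit wording of trigger (b) names neither a source nor a time, so nothing in that sentence keeps session readings out. The monthly review is not limited to survey data and describes no layout by arm or by route of detection. If session findings entered a by-arm comparison, the trial could stop, or the intervention could look harmful, because of detection alone.

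**Working it through.** **Scheduled readings.** Inputs: 30 per arm; three intervention sessions and one control call; one C-SSRS per session.
- First call included: 30 × 3 = 90 v 30 × 1 = 30.
- After the first call, before the survey: 30 × 2 = 60 v 30 × 0 = 0. At an assumed 80% attendance, 48 v 0.

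The imbalance is real and needs no assumption beyond attendance.

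**Where those readings go.** The plan gives them one use, which is referral of participants at risk. The efficacy analysis is a pre-post mixed model with time, condition and their interaction. The discontinuation triggers, as Data & Safety Monitoring states them, use the follow-up survey. The two statements of the rule compare as follows:

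| | Risk/Benefit Assessment | Data & Safety Monitoring |
|---|---|---|
| (a) rise in suicidal behaviour | no source | baseline to follow-up survey |
| (b) intervention worse than control | no source | follow-up survey |

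The first names no rival source. It is the same rule with less detail, on both triggers.

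**Size if session-detected events were counted anyway.** Assume the survey is at day 90, recall is past month (30 days), hazard is constant, true risk p is equal in both arms, and other routes catch a fraction q of events outside the directly covered days. Covered days c are 28 + 30 = 58 (intervention) and 30 (control).

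Expected affected participants = 30 × p × [c + (90 − c) × q] / 90.

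The excess is 30 × p × (28/90) × (1 − q).

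| p = 0.10 | Intervention | Control | Excess |
|---|---|---|---|
| q = 0 | 1.93 | 1.00 | 0.93 |
| q = 0.50 | 2.47 | 2.00 | 0.47 |
| q = 0.75 | 2.73 | 2.50 | 0.23 |
| q = 1 | 3.00 | 3.00 | 0 |

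At 80% independent attendance the early cover is 0.8 × 28 + 0.2 × 0.8 × 14 = 24.64 days, so c = 54.64 and the excess is 0.82, 0.41, 0.21 and 0. At p = 0.05 with full attendance it is 0.47, 0.23, 0.12 and 0.

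**Direction is not fixed.** Everyone enters with ideation in the past month. If 100%, 70% and 50% of readings were positive at day 0, week 2 and week 4 in both arms (assumed), the rate per reading would be (100 + 70 + 50)/3 = 73% for intervention and 100% for control. That statistic would flatter the intervention.

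**Would a separate table help?** Suppose events first detected at an intervention session were moved to their own column. With p = 0.10, q = 1, and every event in the first 28 days first found in session, the remaining column shows 3.0 × 62/90 = 2.07 intervention v 3.00 control at equal risk. The deficit of 0.93 is as large as the biggest excess the table was meant to remove.

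**Survey recall.** If the survey asks only about the past month, it directly covers 30 × 0.10 × 30/90 = 1.0 of 3.0 expected affected participants in each arm. Since-enrolment items would cover 3.0, or 30 × 0.10 × (30 + 0.8 × 60)/90 = 2.6 if 20% of earlier events were forgotten (assumed). This is the same in both arms, and the survey itself is not in the document.

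**The case for a change.** The strongest opposing case is that a rule able to end a trial should name one source wherever it is written, and that the sums above are too kind because they count behavioural events. If positive session readings were tallied as participants ever positive, the gap would be wider. Take independent readings with equal probability of a positive in both arms. At 10% per reading, the expected counts are 8.1 v 3.0 participants. The probability that the intervention count exceeds control is then 0.94, against 0.41 with one survey reading each. For assumed probabilities from 0.02 to 0.30 the ranges are 0.66 to 0.997 and 0.29 to 0.44. Neither statement of the rule has a margin, so a small excess would qualify as greater. The monthly review also sees ideation trends before any survey is due.

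Part of this stands. Session readings are not comparable between arms as ever-positive counts, and the Risk/Benefit sentence is incomplete. But the wider gap needs a tally that no section describes. Independence also overstates it: repeated readings on one person are correlated, and the gap closes if status does not change between readings. The monthly review is a mentoring discussion of safety data with no between-arm test attached. The lack of a margin applies equally to the survey and is a separate matter.

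**Conclusion.** The concern describes the schedule correctly (60 v 0 readings) but identifies no analysis or decision that those readings distort. The complete statement of the rule, in the section devoted to monitoring, uses a survey common to both arms. The shorter statement omits that source for both triggers and contradicts nothing; a reader with both sections fills the gap, and aligning the sentences would be clerical.

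Extra readings are inherent in comparing three sessions with one, and they serve participants' safety. The illustrated excess in affected participants is under one, disappears with full capture by other routes, and reverses for a per-reading rate. A separate table could create a bias of equal size the other way, and new recall items depend on a survey that cannot be seen here.

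This conclusion rests on two readings: that Data & Safety Monitoring supplies the source for the rule, and that the follow-up survey is the 3-month one. The second affects only the illustration. If session readings were ever brought into a between-arm comparison, the conclusion would no longer hold.

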Official Title: Telehealth to Reduce Suicidality and Improve HIV Care Engagement in Tanzania

NCT: NCT04696861

IRB Document Date: 5/13/2024

DUHS IRB Application (Version 1.15)

Approval Date 05/13/2024 NCT04696861

General Information		
*Please enter the full title of your protocol:		
Telehealth to Reduce Suicidality and Improve HIV Care Engagement in Tanzania		
*Please enter the Short Title you would like to use to reference the study:		
Suicidality and Care Engagement in Tanzania * This field allows you to enter an abbreviated version of the Study Title to quickly identify this study.		

Standard Research Summary

Purpose of the Study

Objectives & hypotheses to be tested

The overall objectives of the proposed research are to develop a brief telehealth counseling intervention to provide support for suicidality and HIV care engagement, and to reduce the mental health treatment gap in Tanzania. Duke has longstanding collaborations with Kilimanjaro Christian Medical Centre and affiliated HIV clinics, making this an ideal environment for this work.

The investigators hypothesize that a brief telehealth counseling intervention for people living with HIV and experiencing suicidal ideation will be safe (participants in the clinical trial will not have increased risk of suicidal behavior), acceptable (high patient retention and satisfaction, high fidelity), and will demonstrate preliminary efficacy of the intervention (reduced suicidal ideation, improved care engagement, improved mental well-being).

• Should support the scientific aims of the research

Mental health comorbidities, particularly depression, are key drivers of the global HIV epidemic, contributing to substandard HIV care engagement, reduced quality of life, increased transmission risk, and lower life expectancy among people living with HIV (PLWH).^{1–3} Depression is exceedingly prevalent among PLWH^{4–6} and suicidal ideation is a common response to an HIV diagnosis, making suicide a leading cause of death among PLWH worldwide.^{7,8} However, when PLWH have access to mental health treatment that includes adherence counseling, both mental health and HIV outcomes improve.^{9,10} Thus, there is an urgent need to enhance access to quality mental health treatment that addresses the unique needs of PLWH.^{11,12}

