Aim 1: Identify the desired characteristics of a telehealth intervention for suicidality and HIV care engagement in the Tanzanian clinical context. To refine the intervention model and assess experiences with suicide risk screening and counseling, study personnel will conduct in-depth interviews (IDIs) with stakeholders including PLWH (n=36), clinic administrators (n=20), nurses (n=12), study counsellors (n=4), mental health workers (n=16), and religious leaders (n = 20). For the patient interviews, clinic nurses will assist in identifying adults in HIV care at the study clinics who previously experienced suicidal ideation or completed screening. All study staff will be trained in suicide assessment and safety planning. Administrators and health workers will be recruited from the study clinics. In-depth interviews with healthcare administrators will help inform strategies for future integration of the intervention into the healthcare system, and in-depth interviews with religious leaders will provide insight into their perspectives on the role of religion and spirituality in mental health and suicide prevention, and ways these perspectives might be integrated into the intervention.

Interview guides will be developed with user-centered design in collaboration with the Tanzanian research team and informed by CFIR domains. Participants will first be presented with the core characteristics of the intervention and asked to provide feedback on its adaptability (e.g., potential for tailoring to individual patients, local setting, and acute crisis format), complexity (difficulty of implementation), feasibility (telehealth model), and sustainability (integration into current models of care). Interviews will also explore the outer setting of patient needs and resources, the relative advantage of the intervention compared to other approaches, and external policies and incentives that could impact its scalability. We will also conduct interviews with participants who have completed screening for the study and study counsellors to explore the acceptability of screening, assessment, and counseling. All participants will receive compensation of 10,000 Tanzanian shillings (\$4.50) for their time and costs of participation. Interviews will be conducted in Kiswahili or English by a trained research assistant in a private office and audio recorded for later transcription.

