 Describe endpoints and power calculations. Provide a detailed description of how study data will be analyzed, including statistical methods used, and how ineligible subjects will be handled and which subjects will be included for analysis. Include planned sample size justification. Provide estimated time to target accrual and accrual rate. Describe interim analysis including plans to stop accrual during monitoring. Phase I studies, include dose escalation schema and criteria for dose escalation with definition of MTD and DLT.

Qualitative data will be analyzed using a thematic approach based on grounded theory and the constant comparative method, a rigorous set of inductive procedures to identify and examine themes from textual data in a way that is transparent and reproducible. Interview transcripts will first be summarized in a qualitative memo, including representative quotes, and organized around a priori domains reflecting the components of the interview guides and CFIR. Next, the memos will be uploaded to NVivo software for coding. Within the broader domains, emerging themes from the interviews will be identified and added to a codebook to develop a coding structure. Each memo will be coded by 2 team members, inter-coder agreement will be calculated, and disagreements will be reconciled via consensus discussion with a 3rd team member. After coding, we will produce NVivo queries and analytic memos to synthesize content, compare participant characteristics, and draw deeper meaning on themes. Qualitative results will be synthesized with the input of the Tanzanian research team, developed into at least one research manuscript, and submitted for publication.

Scale validation will include evaluation of internal consistency of each instrument (Cronbach's alpha and item-scale correlation), convergent validity among related measures, and confirmatory factor analysis to assess whether the factor structure of the English version of manuscript is retained in the Tanzaniain clinical sample.

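### Does the 3-month satisfaction mean need a stated denominator and a missing-survey rule before it can be used?

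*Combined protocol and SAP*

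**What the plan says.** The Data Analysis & Statistical Considerations section says that feasibility and acceptability of the intervention "will be described by retention patterns, participant satisfaction, fidelity, and implementation cost". Two of these four components carry a number. Fidelity is acceptable if the mean TQS score is at least 3, scored from 0 to 4. Satisfaction is taken once, "at the 3-month survey and defined as a mean score" of 3 or more, scored from 1 to 4. Retention has no target.

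Under Assignment to condition, participants are "individually randomized to receive either a brief Safety Planning Intervention (n=30), or the 3-session telehealth intervention (n=30"). The largest denominator for the intervention arm is therefore 30.

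The hypothesis, under Objectives & hypotheses to be tested, defines the intervention as "acceptable (high patient retention and satisfaction, high fidelity"), so retention and satisfaction are named together. Under Aim 1, interviews with people who completed screening and with study counsellors are also planned "to explore the acceptability of screening, assessment, and counseling".

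The form's own prompt at the head of the analysis section asks "which subjects will be included for analysis". The answer does not say this for satisfaction.

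**The concern.** A single mean at three months can be computed only from people who are still there and who answer. The plan does not say whether the mean covers one arm or both. Nor does it say whether it covers everyone randomised, those who finished their sessions or those who returned a survey. The mixed-effects model is specified for the efficacy outcomes and does not reach a measure taken once. The interviews do not alter the numeric result.

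People who disliked the counselling may be less likely to come back. If so, respondents overstate satisfaction in the arm, and the threshold could be passed when the whole arm would not pass it. That would matter because acceptability is a main question of this pilot and efficacy is expressly unpowered. Satisfaction is also the only acceptability threshold that participants themselves report. The efficacy analyses are not affected.

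**Working it through.** The plan derives no figure for satisfaction, so there is nothing to reproduce. What can be checked is how far missing surveys could move the result.

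**Inputs from the documents:** 30 randomised to the intervention; threshold 3; scale 1 to 4.

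**Assumed inputs:** number missing *k*, respondent mean *m*, non-respondent mean *s*, and standard deviation (SD). The documents give none of these.

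**Step 1. Whole-arm mean** = ((30 − k)·m + k·s)/30. With k = 6 (20% missing):

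| m | s = 2.0 | s = 2.5 |
|---|---|---|
| 3.1 | (74.4 + 12)/30 = 2.88 | (74.4 + 15)/30 = 2.98 |
| 3.2 | (76.8 + 12)/30 = 2.96 | (76.8 + 15)/30 = 3.06 |
| 3.3 | (79.2 + 12)/30 = 3.04 | (79.2 + 15)/30 = 3.14 |
| 3.5 | (84.0 + 12)/30 = 3.20 | (84.0 + 15)/30 = 3.30 |

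The verdict reverses at 3.1 and 3.2 if non-respondents average 2.0, and only at 3.1 if they average 2.5.

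**Step 2. Missing fraction at which the arm mean equals 3** = (m − 3)/(m − s). For m = 3.1, 3.2, 3.3 and 3.5:

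- s = 2.0: 9.1%, 16.7%, 23.1%, 33.3%. The verdict first reverses at 3, 6, 7 and 11 missing of 30.
- s = 2.5: 16.7%, 28.6%, 37.5%, 50.0%. It first reverses at 6, 9, 12 and 16 missing.

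**Step 3. How strong is the assumption?** The gap between 3.2 and 2.0 is 1.2 points on a scale that spans 3. With an assumed SD of 0.6 or 0.4, that is 2 or 3 SDs. Under exactly that gap with 6 missing, a normal approximation gives a respondent mean of at least 3 with probability 0.95 (SD 0.6) or 0.99 (SD 0.4). The same criterion on all 30 would be met with probability 0.36 or 0.29. So a misleading pass is possible, but it takes a large gap.

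**Step 4. Precision near the threshold.** With 24 respondents the standard error is 0.6/√24 = 0.12 or 0.4/√24 = 0.08. The reversed values at s = 2.0 lie 0.12 and 0.04 below 3, which is at most about one standard error at the larger SD and 1.5 at the smaller. A mean this close to 3 would be uncertain even with every survey returned.

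**Step 5. What a reader can recover.** Given the mean and the number responding, the non-respondent mean that brings the arm down to 3 is (90 − (30 − k)·m)/k. With k = 6 it is 2.6, 2.2, 1.8 and 1.0 for m = 3.1, 3.2, 3.3 and 3.5. No pre-set score is needed.

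**Step 6. What stricter rules would do.** Counting every non-respondent as not satisfied caps the satisfied share at the response rate: 27/30 = 90%, 24/30 = 80% and 21/30 = 70% for 3, 6 and 9 missing. It largely repeats retention. Imputing a low score makes the verdict depend on the score chosen. With m = 3.3 and 6 missing, s = 2.0 gives 3.04 (met), but s = 1.0 gives (79.2 + 6)/30 = 2.84 (not met). With 12 missing and s = 1.0, respondents would need (3 − 0.4 × 1.0)/0.6 = 4.33, above the top of the scale.

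**The case for a change.** The strongest case for a change is that the omission is real and the form asks for exactly this information. Missing surveys are foreseeable: the plan collects outreach preferences for missed sessions and allows for patients who cannot return to the clinic. Retention has no target and no rule ties it to the satisfaction result, so it does not formally guard against a misleading pass. Naming the analysis set would cost a sentence.

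Most of this stands as a description. The set is not named, and "retention patterns" is loose enough that session attendance and survey completion might not coincide. What does not follow is that the analysis would go wrong. The wording concerns acceptability of the intervention, which points to the intervention arm. The questionnaire belongs to the 3-month survey, so, skipped items apart, people lost to that survey are the people without a score. A report that gives retention beside the mean shows the loss. Because the hypothesis requires both high retention and high satisfaction, heavy loss counts against acceptability in its own right. Payments for clinic contacts, text check-ins and remote sessions may also limit loss, though they are not an analysis rule.

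**Conclusion.** The concern describes a gap that analysts fill sensibly, not an error in the plan. An ordinary report would give the intervention-arm mean, the number responding out of 30 and retention, and would word the conclusion as holding among respondents. A reader could then work out the break-even value directly.

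The possible effect is confined to one descriptive statement. It is fragile when the respondent mean is near 3. At 3.5 it stands unless more than a third are missing with an assumed mean of 2.0. If non-respondents are as satisfied as respondents, nothing changes. All of these sizes rest on assumed dropout, scores and SDs, because the documents supply none.

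No progression rule depends on the threshold. Going further, by scoring missing surveys as dissatisfaction or by requiring the mean to survive a chosen low score, would either repeat retention or rest the verdict on a number that reasonable statisticians would dispute. No change to the plan is called for.
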